10.1.7 Auditing and Monitoring

Sponsor-assigned CRAs will conduct regular center visits to the investigational facilities for the purpose of monitoring various aspects of the study, such as assessing subject recruitment, compliance with protocol procedures, completeness and accuracy of data entered into the CRFs, verification of CRF data against original source documents, occurrence of adverse events and the safety and rights of subjects are being protected, and that the study is being conducted in accordance with the currently approved protocol and any other study agreements, ICH GCP, and all applicable regulatory requirements. The investigator must agree to -sponsor-authorized personnel having direct access to the clinical (or associated) files and clinical study supplies (dispensing and storage areas) to ensure compliance with applicable regulations, and the investigator will assist with the sponsor's monitoring activities.

Quality control will occur at each stage of data handling to ensure that all data are reliable and have been processed correctly. The sponsor should ensure oversight of any study related

Clinical Study Protocol: 20200497

Final 1.0 Date: 03 Jun 2021 Page **76** of **87**

duties and functions carried out on its behalf, including study related duties and functions that are subcontracted to another party by the sponsor's contracted CRO(s).

The CRFs should be completed in a timely manner and on an ongoing basis to allow regular review by the CRA. Details describing the strategy, responsibilities, and requirements of the study monitoring are provided in the Study Monitoring Plan.

The purpose of an audit is to assess whether ethics, regulatory, and quality requirements are being fulfilled. The sponsor or its representative may conduct audits at the investigative centers including, but not limited to, drug supply, presence of required documents, the informed consent process, and comparison of CRFs with source documents. Government regulatory authorities may also inspect the investigator during or after the study.

The investigator (or designee) should contact the sponsor/CRO immediately if this occurs. All medical records (progress notes) must be available for audit. The investigator must agree to participate with audits conducted at a convenient time in a reasonable manner.

10.1.7.1 Risk and Quality Tolerance Limits

Perceived risks and quality tolerance limits (QTLs) will be identified and documented before the start of the study.

The sponsor and CRO will review risk control measures periodically to ascertain whether the implemented quality management activities remain effective and relevant. The quality management approach and any important deviations from the predefined QTLs (and remedial actions adopted) will be described in the CSR.

10.1.7.2 Protocol Adherence and Deviations

The investigator and site personnel should conduct the study in compliance with the protocol and should use continuous vigilance to identify and report protocol deviations.

A protocol deviation is any change, divergence, or departure from the study design or procedures defined in the protocol that may be on the part of the investigator, site personnel, or the subject.

Important protocol deviations are a subset of protocol deviations that may significantly impact the completeness, accuracy, and/or reliability of the study data or that may significantly affect a subject's rights, safety, or well-being. For example, important protocol deviations may include

randomizing subjects in violation of key eligibility criteria designed to ensure a specific subject population or failing to collect data necessary to interpret primary endpoints, as this may compromise the scientific value of the study.

The investigator should not implement any deviation from the protocol without agreement from the sponsor and prior review and approval from the IRB/IEC of an amendment, except where necessary to eliminate an immediate hazard to a study subject. In the event of an important protocol deviation, the investigator will discuss the deviation with the sponsor's medical monitor and will come to an agreement as to whether the subject should be withdrawn from the study due to the important protocol deviation.

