7.1 Discontinuation of Investigational Product

Subjects (or a legally acceptable representative) can decline to continue receiving investigational product or procedures at any time during the study but continue participation in the study. If this occurs, the investigator is to discuss with the subject the appropriate processes for discontinuation from investigational product and must discuss with the subject the possibilities for continuation of the Schedule of Assessments (Table 1-1) including different options of follow-up (eg, in person, by phone/mail, through family/friends, in correspondence/communication with other treating physicians, from the review of medical records) and collection of data, including adverse events, and must document this decision in the subject's medical records. Subjects who have discontinued investigational product and/or other protocol required therapies or procedures should not be automatically removed from the study. Whenever safe and feasible, it is recommended that these subjects remain in the study to ensure safety surveillance and/or collection of efficacy data, where possible. Reasons for early removal from -protocol-required investigational product(s) or procedural assessments may include:

- Decision by sponsor
- Lost to follow-up
- Death
- Adverse event
- Subject request
- Protocol deviation
- Noncompliance
- Pregnancy

Final 1.0 Date: 03 Jun 2021 Page **41** of **87**

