7.2 Subject Discontinuation/Withdrawal from the Study

Participation in the study is strictly voluntary. Subjects have the right to withdraw from the study by his/her own request at any time and for any reason without any reprisal, and without prejudice to future medical care by the physician or institution.

Subjects unable to complete the week 12 visit will be discontinued from the study. However, subjects should return and complete EOS visit procedures. The lead-in period will occur from day 1 until randomization at week 12. All enrolled subjects not randomized at week 12 will be considered lead-in failures and the lead-in failure reason will be documented. Subjects terminating early from the study should complete all procedures scheduled for EOS Visit (ie, week 32) within 28 days after withdrawal/discontinuation if possible. Non-responders (defined as subjects achieving less than PASI 50 response at week 12 visit) will be discontinued from the study at week 12. These subjects will be asked to complete EOS Visit procedures.

Withdrawal of consent for a study means that the subject does not wish to receive further protocol required therapies or procedures, and the subject does not wish to or is unable to continue further study participation. Subject data up to withdrawal of consent will be included in the analysis of the study, and where permitted, publicly available data can be included after withdrawal of consent. The investigator is to discuss with the subject appropriate procedures for withdrawal from the study and must document the subject's decision to withdraw in the subject's medical records. If the subject withdraws consent for disclosure of future information, the sponsor may retain and continue to use any data collected before such a withdrawal of consent. If a subject withdraws from the study, he/she may request destruction of any samples taken and not tested, and the investigator must document this in the study center study records and notify the sponsor or designee. Although a subject is not obliged to give his/her reason(s) for withdrawing prematurely from a study, the investigator should make a reasonable effort to ascertain the reason(s), while fully respecting the subject's rights. Subjects who are withdrawn will not be replaced. Subjects who prematurely discontinue from the study cannot subsequently rejoin the study.

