6.3 PK Analysis Sets

PK Concentration Analysis Set

The PK Concentration Analysis Set which will include all randomized subjects who received at least 1 dose of IP post-randomization and have at least 1 reported serum concentration of ABP 501 or Humira on or after the day of randomization. This analysis set will be used for analyses of PK concentrations during the Post- randomization Period according to actual treatment received.

PK Parameter Analysis Set

The PK Parameter Analysis Set consists of all randomized subjects who receive at least one dose post-randomization and who have an evaluable ABP 501 or Humira serum concentration-time profile between weeks 28 and 30. This analysis set will be used for the primary analysis of the primary and secondary PK endpoints and will be analyzed according to actual treatment received.

Per-protocol PK Parameter Analysis Set

The Per-protocol PK Parameter Analysis Set consists of all subjects in the PK Parameter Set who do not have an important protocol deviation during the study that could affect the primary PK endpoints. This analysis set will be used for a sensitivity analysis of the primary PK endpoints and will be analyzed according to actual treatment received.

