9.7.10 Exposure to Concomitant Medication

Prior and concomitant medications will be coded using the latest available World Health Organization Drug Dictionary as of the time of the final analysis.

For the Lead-in Period, concomitant medication use by PT is summarized descriptively for the LTS and for the SAS by actual treatment group.

For the Post-randomization Period, concomitant medication use by PT is summarized descriptively by actual treatment group based on SAS.

Enter Other Analyses

Enter Analyses of Pharmacokinetic or Pharmacodynamic Endpoints

Protocol Number: 20200497

Date: 10FEB2023 Page 34 of 36

Enter Analyses of Clinical Outcome Assessments

Enter Analyses of Health Economic Endpoints

Enter Analyses of Biomarker Endpoints

10. Changes from Protocol-specified Analyses

The definition of PK Parameter Analysis Set could be too restrictive and may result in exclusion of evaluable subjects, and the protocol is not required to be amended. The PK Parameter Analysis Set was changed to consist of all randomized subjects who receive at least one IP dose post-randomization from who receive all assigned IP doses post-randomization, and who have an evaluable ABP 501 or Humira serum concentration-time profile between weeks 28 and 30. The Per-protocol PK Parameter Analysis Set was changed accordingly and consists of all subjects in the PK Parameter Analysis Set who do not have an important protocol deviation during the study that could affect the primary PK endpoints. These changes will also be documented in the Clinical Study Report.

11. Literature Citations / References

12. Prioritization of Analyses

None.

13. Data Not Covered by This Plan

None.

Protocol Number: 20200497

Date: 10FEB2023 Page 35 of 36

14. Appendices

Protocol Number: 20200497

Date: 10FEB2023 Page 36 of 36

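### Protocol 10.1.7.2 allows a randomized subject to be withdrawn from the study for an important deviation alone, a selection the SAP assigns to pre-lock per-protocol sets

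*Protocol*

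**What the plan says.** Protocol 10.1.7.2 defines important protocol deviations and tells the investigator to discuss each one with the medical monitor. The two then "will come to an agreement as to whether the subject should be withdrawn from the study due to the important protocol deviation". The section sets no criteria for that decision. One of its two examples is "randomizing subjects in violation of key eligibility criteria designed to ensure a specific subject population", so the rule reaches subjects who are already randomized.

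Related routes appear elsewhere. Protocol 7.1, under "Reasons for early removal from -protocol-required investigational product(s) or procedural assessments may include", lists protocol deviation and noncompliance. Protocol 7.2 lets the investigator discontinue a subject from the study for noncompliance with procedures or to protect the integrity of the data, among other reasons. Section 7.1 also says that subjects who have stopped product or procedures "should not be automatically removed from the study. Whenever safe and feasible, it is recommended that these subjects remain in the study". Section 7.2 makes withdrawal final: "Subjects who are withdrawn will not be replaced", and they may not rejoin.

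The SAP handles deviations at the analysis stage. Under SAP 6.3 the PK Parameter Analysis Set needs one post-randomization dose and an evaluable week 28 to 30 profile. Only the Per-protocol PK set is restricted to subjects "who do not have an important protocol deviation during the study that could affect the primary PK endpoints". SAP 9.3 requires the per-protocol sets to be final before database lock. SAP Section 10 explains that the primary PK set was widened because its protocol definition "could be too restrictive and may result in exclusion of evaluable subjects".

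**The concern.** Withdrawal from the study and exclusion from an analysis set are different acts. Exclusion is documented, decided before lock and reversible in a sensitivity analysis. Withdrawal ends data collection, so no later analysis can bring the subject back. Section 10.1.7.2 allows withdrawal for the deviation itself, without requiring a safety or consent reason.

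If this is used before week 28, part of the per-protocol selection has already happened by the time the primary PK set is formed. The primary and per-protocol PK analyses then differ less than they should, and their agreement says less about robustness. If withdrawals also differ by arm in number or in kind, the geometric mean ratio (GMR) shifts.

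**Working it through.** **1. What a withdrawn subject loses**

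- *Week 28 to 30 PK.* Withdrawal before week 28 leaves no evaluable profile, so the subject is outside the PK Parameter Analysis Set. SAP 8.3 does not impute missing PK. The end-of-study (EOS) visit in Table 1-1 has a single PK sample, not the serial profile.
- *Week-30 PASI.* Table 1-1 schedules PASI 14 days after the week 28 dose and not at EOS. The Full Analysis Set (FAS) sensitivity analysis uses observed data (SAP 9.6.2.2), so the subject drops out of it. The Per-protocol Efficacy set requires all assigned doses (SAP 6.5), so a subject withdrawn before week 28 leaves that set too, even if the deviation had no bearing on efficacy.
- *Safety and antidrug antibodies (ADA).* Early terminators are asked for one EOS visit within 28 days if possible. It gives adverse events, laboratory tests, one PK and one ADA sample. Missing values are not imputed (SAP 8.3).

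**2. Which deviations can move the primary GMR**

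SAP 5.1 puts subjects who deviate from their assigned regimen into separate actual-treatment groups. SAP 6.3 analyzes the PK set by actual treatment, and SAP 9.5.1.1 compares only the switching and continued-use groups. Therefore:

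- *Non-regimen deviations* (eligibility, prohibited medication, procedural): a subject kept in the study with an evaluable profile counts in the primary GMR. Withdrawal before week 28 removes that subject.
- *Regimen deviations*: read literally, the subject is outside the primary GMR either way. The loss is to FAS efficacy and to safety and ADA follow-up.

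**3. Power: reproducing the plan's figure**

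Inputs from Protocol 9.3: 342 randomized 1:1, 15% loss, CV 53%, true GMR 1, margin 0.80 to 1.25, two one-sided tests at 0.05.

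- SD(log) = √ln(1 + 0.53²) = √0.2476 = 0.4976
- Evaluable: 342 × 0.85 = 290.7, about 145 per arm
- SE = 0.4976 × √(2/145) = 0.0584
- Power ≈ 2Φ(ln 1.25/SE − t) − 1, with ln 1.25 = 0.2231 and t = 1.65. This is 2Φ(2.17) − 1 = 97.0% per endpoint, and 0.970² = 94.0% for both if independent.

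The stated power of at least 90% holds. With greater loss:

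| Loss | Per endpoint | Both, if independent |
|---|---|---|
| 20% | 95.9% | 92.0% |
| 25% | 94.7% | 89.6% |
| 30% | 92.9% | 86.3% |
| 35% | 90.8% | 82.5% |

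**4. Bias: assumed ranges only**

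The documents give no deviation or withdrawal rate. Suppose fractions f_S (switching) and f_C (continued use) are withdrawn, and those subjects would have had r times the geometric mean exposure of the rest of their arm. The GMR estimate is then multiplied by exp[−(f_S − f_C) ln r].

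- *Equal withdrawal in both arms*: the factor is 1, so there is no bias.
- *4 versus 3 of 145, r = 0.5*: exp[(1/145) × 0.693] = 1.005.
- *One-arm worst case, f_C = 0, r = 0.5*: f_S of 1%, 2% and 5% give 1.007, 1.014 and 1.035. At a true GMR of 0.80 and 145 per arm, the chance that one endpoint passes rises from 5.0% to 6.3%, 8.0% and 14.6%.
- *One-arm, r = 0.7*: the same fractions give 5.7%, 6.4% and 9.0%.

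Both endpoints must pass, so the trial-level error is no higher than these. The planned adjustment for weight and week-12 trough is left out. It could absorb part of a difference already visible at week 12, but it would also narrow the interval.

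**The case against.** The sponsor can fairly say that the rule asks whether to withdraw and does not require it. The investigator, sponsor and CRO study team are blinded (Protocol 6.4 and 6.4.1), so there is no obvious route to arm-dependent decisions. Section 7.1 rules out only automatic removal, and a case-by-case discussion is not automatic. Sections 7.1 and 7.2 themselves name deviation, noncompliance and data integrity, so 10.1.7.2 fits them. Efficacy-relevant deviators are outside the main efficacy analysis anyway. A deviation found after the week 30 and EOS visits costs no data.

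Most of this stands, and it disposes of several stronger readings:

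- *A contradiction with 7.1.* The texts pull in different directions on keeping subjects in follow-up, but they do not conflict outright.
- *The SAP's widening of the primary PK set is undone.* SAP 5.1 already keeps regimen deviators out of the compared groups, so this goes too far.
- *Later safety and ADA data are lost.* They are shortened, because the EOS visit is still requested and Protocol 8.9 asks for a final antibody sample.
- *The 15% allowance is threatened.* It already counts study discontinuation before week 28, and per-endpoint power stays above 90% up to about 35% loss.

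What does not fall is the central point. Nothing limits withdrawal to safety, consent or rights, and the missing week 28 to 30 and week-30 data cannot be recovered. Blinding limits differential withdrawal but cannot exclude it, because a deviation may follow from tolerability, loss of response or antibodies.

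**Conclusion.** The concern holds as a matter of selection and missing data. Section 10.1.7.2 permits a selection during conduct, without criteria, that the SAP assigns to per-protocol sets fixed before lock. For the primary GMR the exposure is confined to non-regimen deviations that lead to withdrawal before the PK profile is evaluable. For regimen deviators it is FAS efficacy and safety and ADA follow-up.

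A reader might infer that the similarity conclusion would be biased in favour of passing. The documents do not support that. The direction and size depend on withdrawals differing by arm and on the exposure of those withdrawn, and neither is given. The 14.6% figure is a one-arm worst case with every withdrawn subject at half exposure; balanced withdrawal of similar subjects gives no bias. Nor would a higher chance of passing at a true GMR inside 0.80 to 1.25 show a false conclusion. This is a cheap improvement to the protocol, not a flaw that invalidates the design.

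**What to change.** Replace the withdrawal clause in Protocol 10.1.7.2 with wording to this effect:

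- An important protocol deviation is not in itself a reason to withdraw a randomized subject from the study.
- Scheduled assessments, including week 28 to 30 PK, ADA samples, week-30 PASI and the EOS visit, continue unless consent is withdrawn or invalid, or there is a safety or subject-rights reason.
- Deviations are handled through the per-protocol sets finalized before database lock.

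The exception for invalid consent and subject rights is needed because 10.1.7.2 counts deviations affecting a subject's rights as important. Reconcile 7.1 and 7.2 with this wording, in particular where they list deviation, noncompliance and data integrity. Decisions on investigational product stay with the existing clinical provisions.

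The cost is a protocol amendment with IRB/IEC and regulatory submission (Protocol 10.1.9), and a few subjects with deviations completing visits already scheduled for them. No visit, sample or analysis is added.

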10.1.8 Data Protection

Subjects will be assigned a unique identifier by the sponsor. Any subject records or datasets that are transferred to the sponsor will contain the identifier only; subject names or any information which would make the subject identifiable will not be transferred.

The subject must be informed that his/her personal study-related data will be used by the sponsor in accordance with local data protection law. The level of disclosure must also be explained to the subject.

The subject must be informed that his/her medical records may be examined by Clinical QA auditors or other authorized personnel appointed by the sponsor, by appropriate IRB/IEC members, and by inspectors from regulatory authorities.

10.1.9 Protocol Approval and Amendment

Protocol modifications, except those intended to reduce immediate risk to study subjects, may be made only by the sponsor.

Any permanent change to the protocol must be handled as a protocol amendment. The written amendment must be submitted to the IRB/IEC, and the investigator must await approval before implementing the changes. The sponsor or designee will submit protocol amendments to the appropriate regulatory authorities for approval.

The current version of the ICF will require similar modification if the IRB/IEC, investigator, and/or sponsor, judge the amendment to the protocol to substantially change the study design and/or increase the potential risk to the subject and/or impact the subject's involvement as a study

subject. In such cases, the ICF will be renewed for enrolled subjects before their continued participation in the study.

10.1.10 Study and Site Start and Closure

The study start date is the date on which the first subject is enrolled to the study. The EOS date is defined as the date when the last subject across all centers is assessed or receives an intervention for evaluation in the study (ie, last subject visit) or has withdrawn prematurely, as applicable.

The sponsor designee reserves the right to close the study site or terminate the study at any time for any reason at the sole discretion of the sponsor. Study sites will typically be closed upon study completion. A study site is considered closed when all required documents and study supplies have been collected and a study site closure visit has been performed.

The investigator may initiate study site closure at any time, provided there is reasonable cause and sufficient notice is given in advance of the intended termination.

Reasons for the early closure of a study site by the sponsor or investigator may include but are not limited to:

- Failure of the investigator to comply with the protocol, the requirements of the IRB/IEC or local health authorities, the sponsor's procedures, or GCP guidelines.
- Inadequate recruitment of subjects by the investigator.
- Discontinuation of further investigational product development.

If the study is prematurely terminated or suspended, the sponsor shall promptly inform the investigators, the IECs/IRBs, the regulatory authorities, and any contract research organization(s) used in the study of the reason for termination or suspension, as specified by the applicable regulatory requirements. The investigator shall promptly inform the subject and should assure appropriate subject follow-up.

